
 To evaluate the TTR reduction of patisiran-LNP in hATTR amyloidosis patients with disease progression after OLT 	
 Average of Month 6 and Month 12 TTR percent reduction.
Secondary	

 To evaluate the effect of patisiran-LNP on neuropathy To evaluate the effect of patisiran-LNP on patient reported outcomes including QoL, activities of daily living and autonomic neuropathy symptoms To characterize the effect on nutritional status 	
 Change in the following parameters at 12 months 
 Neurologic impairment (NIS) Patient reported measures of QoL (Norfolk QoL-DN), activities of daily living (R-ODS) and autonomic symptoms (COMPASS-31) Nutritional status (mBMI)
Exploratory	

 To characterize exploratory measures of clinical activity (disease stage, functional status) To evaluate PK To assess for ADA against patisiran-LNP 	
 Change in the following parameters at 12 months 
 Disease stage (PND Score, FAP Stage) Functional status: KPS PK profile of ALN-18328, and the novel lipid excipients DLin-MC3-DMA and PEG₂₀₀₀-C-DMG Frequency and titer of anti-PEG₂₀₀₀-C-DMG ADA

Objectives	Endpoints
Safety	

To evaluate the safety and tolerability of patisiran-LNP in hATTR amyloidosis patients with disease progression after OLT	
Frequency of adverse events

Study Design

This is a global Phase 3b open-label study designed to evaluate the safety, efficacy, and pharmacokinetics (PK) of patisiran-LNP in patients with hATTR amyloidosis with disease progression after liver transplant. The study will consist of a Screening period of up to 42 days, a 12-month treatment period and a 4-week follow up period after the last dose.

Consented eligible patients enrolled in this study will receive 0.3 mg/kg patisiran-LNP intravenously (IV) once every 3 weeks for 12 months. Patients will receive premedications at least 60 minutes before the start of the patisiran-LNP infusion in order to reduce the potential for an IRR with patisiran-LNP.

After the Day 1 visit, patients should return to the clinical site for patisiran-LNP dosing once every 3 weeks. Where applicable country and local regulations allow, eligible patients may receive the patisiran-LNP infusions at home by a healthcare professional trained on the protocol and delivery of premedications and patisiran-LNP.

Safety will be assessed throughout the study. Patients will return to the clinical site for safety evaluations at Week 12, 6 month efficacy visit, and 12 month efficacy visit. Patients will be continually assessed throughout the study for adverse events (AEs). Unscheduled visits for study assessments may occur if deemed necessary by the study personnel.

Efficacy assessments will be performed at baseline, 6 and 12 months.

Number of Planned Patients

Twenty patients are planned for enrollment in this study.

Diagnosis and Main Eligibility Criteria

This study will include adults (≥ 18 years of age) who have received an orthotopic liver transplant for treatment of documented hATTR amyloidosis ≥ 12 months before the date of informed consent, and documented increase in polyneuropathy disability (PND) score (eg, a PND change from I to II, II to IIIA, or IIIA to IIIB) compared to a pre-liver transplant assessment OR a documented increase in PND score between any 2 assessments post-liver transplant, which in the opinion of the Investigator is due to underlying disease progression.

Study Drug, Dose, and Mode of Administration

Patisiran-LNP comprises a small interfering ribonucleic acid (siRNA) which is specific for TTR, and is formulated in a lipid nanoparticle (LNP) for the hepatic delivery following an intravenous (IV) administration. Patisiran-LNP 0.3 mg/kg will be administered as an IV infusion once every 3 weeks. Dosing is based on actual body weight. For patients weighing ≥ 100 kg, the recommended dose is 30 mg.

In order to reduce the potential for an IRR with patisiran-LNP, all patients will receive premedications at least 60 minutes before the start of the patisiran-LNP infusion. Modifications

to lower the corticosteroid dose may be made to the premedication regimen as described further in the protocol.

Non-Alnylam Investigational Product, Dose, and Mode of Administration

Not applicable, open-label study.

Reference Treatment, Dose, and Mode of Administration

Not applicable, open-label study

Duration of Treatment and Study Participation

The duration of treatment with patisiran-LNP is 12 months. The estimated total time on study, inclusive of screening is up to 14.5 months, due to the requirement for an additional 4 weeks of follow-up.

Statistical Methods

Sample size assumptions included normally distributed true TTR percent reduction from baseline of 80% with a standard deviation of 18%. Given these assumptions, a sample size of 16 patients will yield a 95% confidence interval with a half-width of approximately 10%. Assuming a 20% premature discontinuation rate, approximately 20 patients will be enrolled in the study.

The populations (analysis sets) are defined as follows:

- Safety Analysis Set: All patients who received patisiran-LNP. The Safety Analysis Set will be used for the analysis of efficacy and safety assessments.
- Pharmacokinetic Analysis Set: All patients in the Safety Analysis Set who have provided at least one valid post-dose PK concentration value.

The median TTR percent reduction and 95% confidence interval will be estimated using the Hodges-Lehmann method; the TTR percent reduction will also be assessed using the Wilcoxon signed-rank test. Secondary endpoints will be analyzed using summary statistics of observed values and changes from baseline for the neuropathy impairment score (NIS) total score and component scores. Patient reported quality of life and disease burden will be assessed by summary statistics for the Norfolk QOL-DN and R-ODS. Patient reported autonomic neuropathy symptoms will be assessed by descriptive statistics for the COMPASS 31. Summary statistics will be provided for observed values and changes from baseline.

Safety data will be summarized with descriptive statistics. Adverse events will be summarized by System Organ Class (SOC) and preferred term (PT) (all events, related events, and serious events), in addition to being summarized by severity (all events). In addition, summaries will be provided for any AEs leading to discontinuation of study drug or death.

Figure 1: Study Design

Screening Period 42 days	Open Label Treatment Period 12 months	Follow Up Period 4 weeks
------------------------------------	---	------------------------------------

Table 1: Schedule of Assessments

Study Day (±Visit Window)	Notes	Screening	Baseline ^a	Dosing							6-Month Efficacy	Dosing				12-Month Efficacy	Early Termination	Safety Follow Up
		D-42 to -1	Pre-Dose Day 1	D1	W1-2	W3 ±3D	W6 & 9 ±3D	W12 ±3D	W15 to 21 ±3D	W24 ±3D	W25 to WK 26±3D	W27 to W33 ±3D	W36 ±3D	W39 to W51 ±3D	W54 ±3D	W55 to W56	W57	Not applicable
Informed Consent		X																
Inclusion/Exclusion Criteria		X	X															
Medical History	See Section 6.1	X	X															
Demographics		X																
HIV Status Review	Section 6.1.3	X																
Height		X																
NYHA Classification			X															
Karnofsky Performance Status		X								X					X		X	
PND Score and FAP Stage		X								X					X		X	
NIS			X							X					X		X	
Norfolk-DN QoL			X							X					X		X	
R-ODS			X							X					X		X	
COMPASS-31			X							X					X		X	

Table 1: Schedule of Assessments

Study Day (±Visit Window)	Notes	Screening	Baseline ^a	Dosing							6-Month Efficacy	Dosing				12-Month Efficacy	Early Termination	Safety Follow Up
		D-42 to -1	Pre-Dose Day 1	D1	W1-2	W3 ±3D	W6 & 9 ±3D	W12 ±3D	W15 to 21 ±3D	W24 ±3D	W25 to WK 26±3D	W27 to W33 ±3D	W36 ±3D	W39 to W51 ±3D	W54 ±3D	W55 to W56	W57	Not applicable
Echocardiogram with Doppler		X																
12-Lead ECG	See Section 6.1.7	X																
NT-proBNP		X																
mBMI	See Section 6.2.6.		X							X					X		X	
Serum samples for TTR Protein	See Section 6.2.1		X		X	X				X	X			X	X			
Serum samples for anti-drug antibody	See Section 6.3.3.1		X			X				X				X				
Plasma samples for PK	See 2		X	X	X	X				X				X	X	X	.	
Pregnancy Test	See Section 6.3.3.2, Section 6.3.5.7, and Table 3	X	X			X	X	X	X	X	X	X	X	X			X	
Exploratory DNA Sample (optional)	See Section 6.5		X															

Table 1: Schedule of Assessments

Study Day (±Visit Window)	Notes	Screening	Baseline ^a	Dosing							6-Month Efficacy	Dosing				12-Month Efficacy	Early Termination	Safety Follow Up	
		D-42 to -1	Pre-Dose Day 1	D1	W1-2	W3 ±3D	W6 & 9 ±3D	W12 ±3D	W15 to 21 ±3D	W24 ±3D	W25 to WK 26±3D	W27 to W33 ±3D	W36 ±3D	W39 to W51 ±3D	W54 ±3D	W55 to W56	W57	Not applicable	W58 ±3D
Exploratory Biomarkers (plasma, serum)		X									X				X				
Full Physical Exam	See Section 6.3.2	X									X				X		X		
Symptom-Directed Physical Exam	See Section 6.3.2		X																
Vital Signs	See Section 6.3.1	X	X	X		X	X	X	X	X	X	X	X	X	X		X		
Serum samples for Vitamin A	See Section 6.1.1	X																	
Serum Chemistry, including LFTs	See Section 5.2.4.1	X	X (albumin only)					X			X		X		X		X		
Hematology		X						X			X		X		X		X		
Adverse Events	See Section 6.3.5.2				Continuous														
Concomitant Medications and Procedures	See Section 5.3	X			Continuous														
Liver Allograft Status	See Section 6.3.4	X						X			X		X		X		X		

Table 1: Schedule of Assessments

		Screening	Baseline ^a	Dosing							6-Month Efficacy	Dosing				12-Month Efficacy	Early Termination	Safety Follow Up	
				D-42 to -1	Pre-Dose Day 1	D1	W1-2	W3 ±3D	W6 & 9 ±3D	W12 ±3D		W15 to 21 ±3D	W24 ±3D	W25 to W26 ±3D	W27 to W33 ±3D				W36 ±3D
Study Day (±Visit Window)	Notes																		
Weight	See Section 6.1.4		X	X		X	X	X	X	X	X	X	X	X	X	X		X	
Premedication and Study Drug Administration	Phone contact for home infusions only			X		X	X	X	X	X		X	X	X	X				

Abbreviations: COMPASS=Composite Autonomic Symptom Score; DNA=deoxyribonucleic acid; ECG=electrocardiogram; FAP=familial amyloidotic polyneuropathy; HIV=human immunodeficiency virus; LFT=liver function test; M=month; mBMI=modified body mass index; NIS=neurological impairment scale; NYHA=New York Heart Association; NT-proBNP=N-terminal prohormone of B-type natriuretic peptide; PK=pharmacokinetic; PND=paroxysmal nocturnal dyspnea; QoL= quality of life; R-ODS=Rasch-built Overall Disability Scale; TTR=transthyretin; W=week.

Notes: The Screening visit must be performed within 42 days before the first dose of study drug (Day 1).

Early termination visit should occur within 7 days of the decision to stop participating in the study.

Table 2: Pharmacokinetic Time Points

Study Visit	Day 1	Week 1-2	Week 3	Week 24	Week 54	Week 55-56	Week 57
Pre-Dose	X		X	X	X		
End of Infusion	X			X	X		
4 ± 1 h post EOI	X				X		
24 ± 4 h post EOI	X				X		
72 ± 6 h post EOI	X				X		
Day 7 to Day 14 post EOI		X				X	
Day 21 post EOI							X

TABLE OF CONTENTS

PROTOCOL SYNOPSIS	4
TABLE OF CONTENTS.....	13
LIST OF TABLES	16
LIST OF FIGURES	16
LIST OF ABBREVIATIONS AND DEFINITIONS OF TERMS.....	17
1. INTRODUCTION.....	19
1.1. Disease Overview	19
1.2. Patisiran-LNP (ALN-TTR02).....	20
1.3. Study Design Rationale	20
1.4. Dose Rationale.....	21
1.5. Benefit-Risk Assessment.....	21
2. OBJECTIVES AND ENDPOINTS.....	23
3. INVESTIGATIONAL PLAN.....	23
3.1. Summary of Study Design.....	23
3.2. Duration of Treatment	24
3.3. Duration of Study Participants.....	24
3.4. Number of Planned Patients	24
3.5. Safety Review Committee	24
4. SELECTION AND WITHDRAWAL OF PATIENTS.....	24
4.1. Inclusion Criteria	24
4.2. Exclusion Criteria	25
4.3. Removal from Study Drug or Assessment	27
4.3.1. Discontinuation of Study Drug or Declining Procedural Assessments	27

IB	Investigational Brochure
INR	International normalized ratio
IRB	Institutional Review Board
IRR	Infusion related reaction
IV	Intravenous
LFT	Liver function test
LNP	Lipid nanoparticle
MedDRA	Medical Dictionary for Regulatory Activities
mBMI	Modified body mass index
NIS	Neuropathy impairment score
NYHA	New York Heart Association
OLT	Orthotopic liver transplantation
os	Oral suspension

Abbreviation	Definition
PEG ₂₀₀₀ -C-DMG	(R)-methoxy-PEG ₂₀₀₀ -carbamoyl-di-O-myristyl-sn-glyceride
PK	Pharmacokinetic
PND	Paroxysmal nocturnal dyspnoea
PO	By mouth
RNAi	Ribonucleic acid interference
ULN	Upper limit of normal
SAE	Serious adverse event
SAP	Statistical analysis plan
siRNA	Small interfering RNA
SmPC	Summary of product characteristics
TTR	Transthyretin
wt	Wild type

1. INTRODUCTION

1.1. Disease Overview

Hereditary transthyretin-mediated amyloidosis (hATTR amyloidosis) is a rare autosomal dominant, systemic disease caused by a mutation in the transthyretin (TTR) gene leading to the extracellular deposition of amyloid fibrils containing both mutant and wild type (wt) TT [Yazaki 2000; Gillmore 2006]. There are more than 120 reported TTR genetic mutations associated with hATTR amyloidosis, and almost all patients are heterozygous for the mutated TTR allele [Connors 2003; Ando 2013]. The most common genotype is the valine to methionine mutation at position 30 (V30M), accounting for approximately 50% of cases worldwide, and occurring primarily in families with heritage from Portugal, Sweden, Japan, and Brazil [Ando 2013; Ando 2005; Gertz 2015].

The cardinal manifestations of hATTR amyloidosis are polyneuropathy and cardiomyopathy. The clinical manifestations of the length-dependent, symmetrical polyneuropathy are the result of amyloid-mediated injury to large and small peripheral nerve fibers [Ando 2013; Plante-Bordeneuve 2011; Benson 2007]. Sensory abnormalities include painful dysesthesias in the feet and hands, and loss of sensation leading to thermal burns involving the feet and hands and to joint injury in the lower limbs. Progressive muscle atrophy and motor weakness in both lower and upper limbs lead to impaired ambulation and inability to perform other activities of daily living, such as being able to hold eating utensils or a drinking glass, or button a shirt or zip up a coat. Autonomic dysfunction results in debilitating orthostatic hypotension, severe gastrointestinal symptoms (including early satiety, chronic nausea/vomiting, and both diarrhea and constipation), bladder dysfunction with recurrent urinary tract infections, and cardiac arrhythmias. Cardiac infiltration with amyloid leads to heart wall thickening and cardiomyopathy characterized by heart failure due to diastolic and systolic dysfunction, and conduction disturbances and arrhythmias [Ando 2013; Benson 2007; Carvalho 1992; Soares 2005; Connors 2004]. This constellation of progressive morbidity from amyloid infiltration results in severe disability, and wasting due to gastrointestinal malabsorption, malnutrition, and cardiac cachexia. Death usually results from heart failure (including sudden death caused by ventricular arrhythmias or electromechanical dissociation) or infection. The median survival is 4.7 years following diagnosis [Yazaki 2000; Plante-Bordeneuve 2011] with a reduced survival (3.4 years) for patients presenting with cardiomyopathy [Yazaki 2000; Gertz 1992; Sattianayagam 2012].

The liver is the primary source of TTR, and liver transplantation is used in some patients for treatment of hATTR amyloidosis [Stangou 2004]. More than 2000 patients have been transplanted in the world since 1990, however, morbidity and mortality are substantial. Patients require life-long immunosuppressive medications, with their attendant risks of infection and renal injury. One-year mortality rates of up to 10% have been reported [Okamoto 2009; Bispo 2009; Herlenius 2004].

Liver transplantation eliminates mutant TTR from the circulation, however, wt TTR is produced by the liver allograft. Disease progression occurs in at least one third of hATTR amyloidosis patients after a liver transplant, presumably due to continued deposition of wt TTR protein from the transplanted liver [Reines 2014; Adams 2013].

There is a need for a safe and effective treatment for patients who have disease progression following liver transplantation. By reducing mutant and wt TTR, patisiran-lipid nanoparticle (LNP) is anticipated to prevent disease progression in patients with hATTR amyloidosis who have progressive disease following orthotopic liver transplant (OLT).

1.2. Patisiran-LNP (ALN-TTR02)

Patisiran-LNP comprises a small interfering ribonucleic acid (siRNA) which is specific for TTR, and is formulated in a lipid nanoparticle (LNP) for the hepatic delivery following an intravenous (IV) administration [Akinc 2010; Coelho 2013]. It is designed to significantly suppress liver production of both wt and mutant forms of TTR, thereby having the potential to reduce amyloid formation and provide clinical benefit to patients with hATTR amyloidosis.

The nonclinical pharmacology, pharmacokinetics (PK), and toxicology of patisiran-LNP were evaluated in a series of in vitro and in vivo studies that have enabled chronic dosing in clinical studies. A summary of the nonclinical data can be found in the patisiran-LNP Investigator's Brochure (IB). The clinical development program for patisiran-LNP consists of 6 studies including 2 Phase 1 studies in healthy volunteers (Studies ALN-TTR02-001 and ALN-TTR02-005) and 4 studies in patients with hATTR amyloidosis with polyneuropathy (Studies ALN-TTR02-002, ALN-TTR02-003, ALN-TTR02-004, and ALN-TTR02-006). All of the studies have been completed, with the exception of the ongoing, global open-label extension Study 006 which is evaluating the long-term safety and efficacy of patisiran-LNP in patients with hATTR amyloidosis. Patisiran-LNP reduced or halted neuropathy progression across motor, sensory and autonomic domains, with association with degree of TTR reduction, and provided evidence of favorable changes on exploratory cardiac endpoints.

On 10 August 2018, US FDA approval was granted for the treatment of the polyneuropathy of hATTR amyloidosis in adults. The Committee for Medicinal Products for Human Use adopted a positive opinion for the treatment of hATTR amyloidosis in adult patients with Stage 1 or Stage 2 polyneuropathy, and the European Commission Decision was granted on 27 August 2018.

1.3. Study Design Rationale

This is a global Phase 3b open-label study designed to evaluate the safety, efficacy, and PK of patisiran-LNP in patients with hATTR amyloidosis with disease progression after liver transplant. The primary endpoint for the study is the average TTR percent reduction at Month 6 and Month 12.

The open-label design is supported by previous studies, including a pivotal Phase 3 double-blind, placebo-controlled study. The clinical benefits seen in the pivotal Phase 3 Study ALN-TTR02-004 (APOLLO) were observed in association with an 80% reduction of TTR with patisiran within 10 to 14 days after a single dose, which was maintained over the duration of the 18-month study compared to no change with placebo. The primary efficacy endpoint in the current study, TTR reduction, is an objective measurement and not susceptible to bias of clinical study center staff or study patients and therefore does not require a blinded placebo group for accurate interpretation.

All patients in this study will receive patisiran-LNP treatment. The study will consist of a 12-month treatment period and a 4-week follow up period after the last dose. The 12-month treatment duration will enable collection of safety and efficacy data in patients with hATTR amyloidosis with disease progression after liver transplant. Previous trials support the 12-month duration, since beneficial effect on TTR reduction and efficacy endpoints including neuropathy impairment score and Norfolk QoL-DN score are evident by 9 months [Adams 2018].

1.4. Dose Rationale

The patisiran drug substance is a novel siRNA that is delivered by a LNP. The LNP facilitates siRNA delivery into hepatocytes via an ApoE dependent process. Upon internalization into hepatocytes via endocytosis, the LNP disintegrates, releasing the TTR-targeting siRNA ALN-18328 into the cytoplasm, where it reduces the production of wt and mutant TTR mRNA via the endogenous mechanism of ribonucleic acid interference (RNAi). A transplanted liver is anticipated to have a similar mechanism of LNP uptake and subsequent TTR mRNA gene silencing as native liver in hATTR patients.

The 0.3 mg/kg dose of patisiran-LNP once every 3 weeks was selected based on dose-response analysis for TTR reduction from 3 Phase 1 and Phase 2 studies. This dose was confirmed by the pivotal Phase 3 Study ALN-TTR02-004.

To minimize the risk of IRRs, patients must receive premedication prior to dosing with patisiran. Patients will receive the following premedications at least 60 minutes before the start of the patisiran-LNP infusion:

- Intravenous dexamethasone (10 mg) or equivalent
- Oral paracetamol/acetaminophen (500 mg) or equivalent
- Intravenous H2 blocker (ranitidine 50 mg, famotidine 20 mg, or equivalent other H2 blocker dose)
- Intravenous H1 blocker: diphenhydramine 50 mg (or equivalent other IV H1 blocker available at the study site). Hydroxyzine 25 mg per oral suspension (os) by mouth (PO) or fexofenadine 30 mg or 60 mg PO or cetirizine 10 mg PO may be substituted for any patient who does not tolerate IV diphenhydramine or other IV H1 blocker

These are the same premedications that were used in previous clinical trials.

1.5. Benefit-Risk Assessment

Patisiran-LNP obtained marketing approval in the US and EU based on the overall favorable risk-benefit profile in previous clinical studies, demonstrating improvement in outcomes of neuropathy, quality of life, activities of daily living, and nutritional status in hATTR patients with polyneuropathy. Previous clinical trials have shown a sustained mean serum TTR reduction of approximately 80% and a reduction of toxic misfolded TTR oligomers. The Phase 2 open label extension study showed evidence of improvement of neurologic impairment at 24 months, as assessed by the mNIS+7 [Adams D 2017]. The randomized, placebo-controlled Phase 3 study met its primary efficacy endpoint (change from baseline in mNIS+7 at 18 months) and all

secondary endpoints. Both studies had an acceptable safety profile with similar risks. Similar benefits are expected in patients who have disease progression post liver transplant.

Infusion-related reactions (IRRs) have been observed in patients treated with patisiran-LNP. To minimize the risk of IRRs, all patients must receive premedication before dosing with patisiran-LNP (Section 5). The infusion may be interrupted or slowed if an infusion related reaction (IRR) occurs (Section 5.2.2).

Patisiran-LNP is contraindicated in patients with a history of severe hypersensitivity (eg, anaphylaxis) to patisiran-LNP or any of the excipients.

Adverse drug reactions reported at a frequency of $\geq 1/10$ (very common) in clinical trial were IRR and peripheral edema.

Detailed information about the known and expected benefits and risks and reasonably expected adverse events of patisiran-LNP may be found in the current edition of the IB. The IB is to be used as the reference safety information for this study. It will be supplemented by the summary of product characteristics (SmPC) in regions where there is an approved label.

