5.2.3. Suggested Guidelines for Management of Infusion-Related Reactions

In the event of an IRR, the infusion of patisiran-LNP may be slowed or stopped and the patient closely monitored until resolution of the reaction. Drugs that may be used to facilitate resolution and permit resumption of patisiran-LNP administration include, but are not limited to: paracetamol/acetaminophen (or equivalent), additional histamine H1/H2 receptor antagonists (eg, ranitidine), NSAIDs, adrenaline, supplemental oxygen, IV fluids, and/or corticosteroids.

Following resolution of a mild or moderate IRR that required interruption of the patisiran-LNP infusion, resumption of administration may occur at the Investigator's discretion at a slower infusion rate for that dose and for all subsequent doses of patisiran. If the infusion is delayed, the infusion should be completed no more than 16 hours after preparation of the solution for infusion.

Patisiran-LNP administration should not be resumed for any patient following a severe IRR until the case is discussed with the Medical Monitor.

If after consultation with the Medical Monitor it is agreed that an individual patient's steroid premedication should be increased then the following steps are recommended:

- If the IRR occurred while the patient received 10 mg intravenous dexamethasone or equivalent at least 60 minutes before the infusion and did not resolve with slowing of the infusion rate, then the patient should be increased by multiples of 5 mg intravenous dexamethasone or equivalent at least 60 minutes before the infusion and/or 5 mg oral dexamethasone or equivalent the night before the intravenous infusion.
- Increased dose of premedication steroids should NOT exceed the combination of 20 mg intravenous dexamethasone or equivalent on the day of infusion and 8 mg oral dexamethasone or equivalent taken the night before the infusion.
- If the IRR occurred while the patient received less than 10 mg intravenous dexamethasone or equivalent, then the patient should return to the prior dose of intravenous dexamethasone or equivalent that did not result in an IRR.

Patients will be instructed to call the Investigator if they experience symptoms such as fever, chills, myalgia, or nausea/vomiting after discharge from the site. For categorization of IRRs, see Section 10.5.

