10.5. Categorization of Infusion-Related Reactions

Signs and symptoms of an IRR usually develop during or shortly after drug infusion and generally resolve completely within 24 hours of completion of infusion. Signs/symptoms may include: allergic reaction/hypersensitivity (including drug fever), arthralgia (joint pain), bronchospasm, cough, dizziness, dyspnea (shortness of breath), fatigue (asthenia, lethargy, malaise), headache, hypertension, hypotension, myalgia (muscle pain), nausea, pruritus/itching, rash/desquamation, rigors/chills, sweating (diaphoresis), tachycardia, urticaria (hives, welts, wheals), vomiting.

Categorization of IRRs is as follows:

Categorization	Description
Mild	Mild reaction: infusion may be continued; if intervention is indicated it is minimal and additional treatment (other than paracetamol for delayed reactions) is not required.
Moderate	Moderate reaction: requires treatment including more intensive therapy (eg, IV fluids, nonsteroidal anti-inflammatory drug [NSAIDs]) in addition to infusion interruption but responds promptly to medication. Treatment is indicated for ≤ 24 hours.
Severe	More than moderate reaction: not rapidly responsive to medication or to interruption of infusion; and/ or prolonged (treatment is indicated for >24 hours); recurrence of severe symptoms following initial improvement.

Protocol Administrative Change 1
ALN-TTR02-008

An Open-label Study to Evaluate Safety, Efficacy and Pharmacokinetics (PK) of Patisiran-LNP in Patients with Hereditary Transthyretin-mediated Amyloidosis (hATTR amyloidosis) with Disease Progression Post-Orthotopic Liver Transplant

Purpose: The primary purpose of this administrative letter is to clarify some inconsistencies in the ALN-TTR02-008 original protocol, dated 07 Oct 2018. The clarifications are specified below; added text is **bold** font and deleted text is indicated by ~~strikethrough~~.

Section 5.2.2.1: Home infusion, page 31

There was an error in the naming of the Weekly clinical site visits in this section that has been corrected as shown for consistency with the dates provided in the Schedule of Assessments:

Home infusion will be allowed if approved by local regulatory authorities. Home infusions are allowed if the patient has tolerated at least 3 infusions well in the clinic.

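### Section 1.5 bars patisiran-LNP after severe hypersensitivity, but the reaction rules in 5.2.3 make no exception for it, and Severe in 10.5 has no life-threatening criterion

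*Protocol*

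**What the plan says.** Protocol Section 1.5 sets the bar: "Patisiran-LNP is contraindicated in patients with a history of severe hypersensitivity (eg, anaphylaxis) to patisiran-LNP or any of the excipients". The entry, dosing and stopping sections do not repeat it.

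Section 5.2.3 holds the rules for a reaction in progress:

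- Treatment: "Drugs that may be used to facilitate resolution and permit resumption of patisiran-LNP administration include" a list that closes with "NSAIDs, adrenaline, supplemental oxygen, IV fluids, and/or corticosteroids".
- Mild or moderate reaction: "Following resolution of a mild or moderate IRR that required interruption of the patisiran-LNP infusion, resumption of administration may occur", at the Investigator's discretion and at a slower rate.
- Severe reaction: "Patisiran-LNP administration should not be resumed for any patient following a severe IRR until the case is discussed with the Medical Monitor".
- Grading: "For categorization of IRRs, see Section 10.5".

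Section 10.5 brings hypersensitivity within the IRR definition. Its list of signs begins "Signs/symptoms may include: allergic reaction/hypersensitivity (including drug fever". Moderate there means treatment plus interruption, with a prompt response and no more than 24 hours of treatment. Severe means a poor response to medication or interruption, treatment beyond 24 hours, or return of severe symptoms after initial improvement.

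Section 6.3.5.2 makes every IRR an adverse event, and the general severity scale in Section 6.3.5.1 places life-threatening consequences and the need for urgent intervention under Severe. Section 4.3.1 lists an adverse event among the reasons for stopping study drug, but only pregnancy carries a mandatory immediate stop. Administrative Change 1 and the SAP leave all of this unchanged.

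**The concern.** The bar on further dosing sits in the benefit-risk introduction, while the section that staff would turn to during a reaction describes routes back to dosing. A patient who has just had anaphylaxis to the study drug has, from that moment, the history that Section 1.5 describes. Section 5.2.3 does not say so, and the scale it points to does not use threat to life to separate Moderate from Severe.

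The decision at stake is whether to restart the interrupted infusion. If the reaction is graded Moderate, no second opinion is required before restarting. Some infusions may be given at home after three well-tolerated clinic infusions (Section 5.2.2.1), and there is no safety review committee (Section 3.5), so the reaction rules should be complete where they stand.

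**Working it through.** The plan attaches no figure to this point, so there is none to reproduce. The check takes one case through each rule in turn.

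**Case.** Anaphylaxis occurs during an infusion. The infusion is interrupted, adrenaline and IV fluids are given, the reaction resolves promptly, treatment lasts less than 24 hours and symptoms do not return.

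| Rule | Applied to the case | Result |
|---|---|---|
| 10.5, sign list | Hypersensitivity is a listed sign | It is an IRR, so 5.2.3 applies |
| 10.5, Moderate | Treatment, interruption, prompt response, at most 24 hours: all met | Fits Moderate |
| 10.5, Severe | Poor response, more than 24 hours, recurrence: none met | Specific Severe criteria not met |
| 5.2.3, if Moderate | Investigator's discretion, slower rate | May resume without Medical Monitor discussion |
| 6.3.5.1 | Life-threatening, urgent intervention | Severe adverse event |
| 5.2.3, if Severe | Medical Monitor discussion first | May resume after discussion |
| 4.3.1 | Adverse event is a possible reason to stop | No mandatory stop |
| 1.5 | Severe hypersensitivity to the drug | Further drug contraindicated |

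Two things follow. First, the two scales give different grades to the same event, and nothing says which one governs resumption; the cross-reference in 5.2.3 leads to 10.5. Second, settling the grade is not enough. Even as Severe, the case reaches only a consultation requirement in 5.2.3, whereas 1.5 requires that dosing not continue.

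**Later infusions.** Inputs: dosing every 21 days with ±3-day windows (Table 1), and serious adverse events (SAEs) reported within 24 hours of staff learning of them (6.3.5.4). The shortest gap between two scheduled infusions is 21 − 3 − 3 = 15 days. Taking off 1 day for the report leaves 15 − 1 = 14 days. If staff learn of the event on the infusion day and report it as serious, the Sponsor knows at least 14 days before the next scheduled dose. That leaves time to apply 1.5 and discontinue. The exposed decision is therefore mainly the restart of the same infusion.

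**The case against.** The strongest reply is that the protocol already forbids the outcome. Section 1.5 is protocol text without exceptions, and Section 8.1 requires conduct in accordance with the protocol. A specific bar can be read together with a general permission. The heading of 5.2.3 calls its content suggested guidelines, its verbs are permissive, and the sentence on severe reactions is a prohibition that sets a minimum condition. Adrenaline is listed to help resolve a reaction as much as to allow a restart. In 10.5 the examples of Moderate treatment are IV fluids and anti-inflammatory drugs, and Severe is introduced as anything more than moderate, so a sensible reader would grade anaphylaxis as Severe. The general scale would record it as Severe, and the SAE definition would capture it, whatever 10.5 says. Sections 4.3 and 4.3.1 already let the Investigator or Sponsor stop the drug. The Investigator's Brochure, product labelling, Pharmacy Manual and Study Manual are not among the documents and may instruct sites directly.

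Most of this stands. A reader might infer that the protocol directs or entitles staff to re-dose after anaphylaxis; for the reasons just given, the documents do not support that. The reply does not supply the missing exception in 5.2.3, the missing threat-to-life wording in 10.5, or a statement of which scale controls resumption. It relies on the reader to recall 1.5 and to override the literal categories during an emergency.

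**Conclusion.** The point holds as an inconsistency in the protocol's own text: 5.2.3 and 10.5, followed literally, can reach a result that 1.5 rules out. It is minor. Section 1.5 gives a frequency class of at least 1/10 for IRRs in general but no rate for severe hypersensitivity, so no patient count can be computed; that the event is rare is an assumption. No sample-size or analysis figure changes. The conclusion rests on reading a reaction during the study as a history of hypersensitivity, and it makes no claim about what unseen site manuals say.

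Two further readings are tempting and should not be drawn.

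- A reader might infer a material gap in the entry criteria, since no exclusion in Section 4.2 names hypersensitivity. Exclusion 4 already removes everyone with past patisiran-LNP use, two of the four lipid excipients are described as novel, and exclusions 19 and 20 leave room for judgement. What remains is close to empty.
- A reader might set the limit that "the infusion should be completed no more than 16 hours after preparation of the solution for infusion" beside the 24-hour SAE reporting deadline and infer an unprotected interval. Both are upper limits, and SAE reporting is not designed to control a bedside restart. The comparison measures no risk.

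**What to change.** 1. In Section 5.2.3, state that after anaphylaxis or other severe hypersensitivity to patisiran-LNP the infusion is not resumed and study drug is permanently discontinued, in line with Section 1.5. Put a matching line in Section 4.3.1 next to the pregnancy sentence, and say there that study assessments continue.
2. In Section 10.5, add to Severe: anaphylaxis or any life-threatening reaction, regardless of speed of response. This brings the IRR scale into line with Section 6.3.5.1 on threat to life.

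The cost is amendment wording. The only patients affected are those whom Section 1.5 already bars from further drug, and no change to the SAP is needed.
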